4.2.3 Safety Outcomes

- Death, clinical organ failure or serious infections defined by development of any one or more of the following clinical events after trial entry and through Day 60 (see PIM for criteria for what constitutes each of these conditions). These are also referred to as protocol-defined anticipated clinical events (PDACEs); see Section 10.2.7.
 - a. Worsening respiratory dysfunction:
 - 1.Respiratory failure defined as receipt of high flow nasal oxygen or noninvasive ventilation, invasive mechanical ventilation, or ECMO, above the categorical level of respiratory support at enrollment
 - b. Cardiac and vascular dysfunction:
 - 1. Myocardial infarction
 - 2. Myocarditis or pericarditis
 - 3. CHF: new onset NYHA class III or IV, or worsening to class III or IV
 - 4. Hypotension requiring institution of vasopressor therapy
 - c. Renal dysfunction:
 - 1. New requirement for renal replacement therapy
 - d. Hepatic dysfunction:
 - 1. Hepatic decompensation
 - e. Neurological dysfunction
 - 1. Acute delirium
 - 2. Cerebrovascular event (stroke, cerebrovascular accident [CVA])
 - 3. Transient ischemic events (i.e., CVA symptomatology resolving within <24 hours)
 - 4. Encephalitis, meningitis or myelitis
 - f. Hematological dysfunction:
 - 1. Disseminated intravascular coagulation
 - 2. New arterial or venous thromboembolic events, including pulmonary embolism and deep vein thrombosis
 - 3. Major bleeding events (>2 units of blood within 24 hours, bleeding at a critical site (intracranial, intraspinal, intraocular, intrathoracic, pericardial, intraabdominal, pelvic, intra-articular, intramuscular with compartment syndrome, or retroperitoneal), or fatal bleeding).

Version 1.0, 11th November 2022 US IND# 162149

g. Serious infection:

Intercurrent, at least probable, documented serious disease caused by an infection other than the qualifying respiratory pathogen, requiring antimicrobial administration and care within an acute-care hospital

- h. Death
- 2. Clinical organ failure or serious infections (Items 1.a. through 1.g above)
- 3. A composite of cardiovascular events (outcomes listed above in safety items 1.b.1, 1.e.2 and 1.e.3) and thromboembolic events (1.f.2)
- 4. Safety and tolerability as measured by:
 - a. A composite of SAEs, clinical organ failure or serious infections (PDACEs; see safety item 1 above) or death through Day 5 and 28. Grade 3 and 4 clinical adverse events will also be included in an additional composite for trials in which they are collected (see Section 10.3.2).
 - b. Allergic reaction of any severity judged to be due to the investigational agent
 - c. Infusion-related reactions of any severity and percentage of participants for whom the infusion was interrupted or stopped prior to completion where applicable
 - d. Premature stopping of planned course of a trial intervention, and reasons for stopping where applicable.
 - e. Adverse events of special interest (AESIs) identified in a given trial
 - f. A composite of SAEs, clinical organ failure or serious infections (PDACEs; see safety outcome 1 above) or death through Day 60
 - g. A composite of hospital readmissions or death through the end of follow-up

Note that the evaluation of safety outcome 4.g is not protected by randomization, as its occurrence is conditional on being discharged alive from the initial hospital admission during which randomization occurred.

5 Objectives

5.1 Primary Objectives

The primary objective of the STRIVE platform is to facilitate the efficient and rigorous execution of randomized clinical trials investigating the safety and efficacy of therapeutic interventions or strategies for acute respiratory infections among hospitalized adults. Each trial within STRIVE will have its own objectives outlined in its trial-specific appendix. The primary objective for each trial will be to compare efficacy of the intervention or strategy under investigation with control for the chosen primary outcome among participants randomized in that trial.

5.2 Secondary Objectives

Secondary objectives for each STRIVE trial will include the evaluation of secondary outcomes (section 4.2), evaluation for heterogeneity of treatment effect, and the enhancement of a pathophysiologic understanding of severe respiratory infections through the collection and analysis of biospecimens.

Version 1.0, 11th November 2022

US IND# 162149

Characteristics considered for heterogeneity of treatment effect evaluations will include:

- participant age
- participant sex, race, and ethnicity
- participant comorbidities
- duration of illness prior to randomization
- severity of illness at randomization
- therapies and vaccines received before randomization
- geographic location
- baseline laboratory measurements, such as presence of neutralizing antibodies against the pathogen of interest and pathogen subtypes.

6 Study Design

6.1 Overview

STRIVE is a master protocol to evaluate the comparative efficacy and safety of antimicrobial, passive immunity, host-response, and supportive care treatments for hospitalized patients with respiratory infections or syndromes of global impact including but not limited to COVID-19 and influenza. This master protocol provides an efficient strategy for the evaluation of multiple interventions across classes and allows the evaluation of concomitant and sequential treatments to inform a strategy to improve recovery from the respiratory infection or syndrome.

In STRIVE, a trial is a study that is designed to answer a specific question about the efficacy and safety of one or more interventions or strategies. Individual trials are designed to investigate one primary question each and will not continue after that primary question has been answered, unless additional follow-up is required by regulators. **STRIVE is designed to contain multiple trials actively enrolling patients at the same time and for trials to be dropped and added iteratively over time.** The details of each trial will be described in a trial-specific appendix to the master protocol.

In general, the STRIVE platform will consider the following four trial types:

- (1) trials of pre-licensure, investigational agents versus placebo
- (2) trials of approved agents used off-label (i.e., repurposed agents) compared to placebo or other standard of care
- (3) trials of comparative effectiveness of multiple agents
- (4) sequential multiple assignment randomized trials (SMART).

The STRIVE platform may have a number of trials ongoing at any given time. To improve efficiency and scientific rigor, these trials may share participants either through co-enrollment (i.e., participant is enrolled in multiple STRIVE trials) or through a shared control/placebo group across multiple trials. Because the STRIVE protocol permits study of a variety of classes of agents across the spectrum of disease severity for different respiratory pathogens using a variety of trial types, the approach to co-enrollment and shared control/placebo is also flexible.

Version 1.0, 11th November 2022

US IND# 162149

We describe the general approach to co-enrollment in Section 6.1.1 and how to randomize participants when they are eligible and consent to multiple trials in Section 6.2.

6.1.1 Co-enrollment

In general, we propose an inclusive approach to co-enrollment across trials, where appropriate. Appropriateness criteria include capacity to meet the requirements of (1) safety, (2) scientific rigor, and (3) regulatory reporting for adverse events. Each of these is addressed in turn, while emphasizing the important role of patient autonomy in assessment of co-enrollment.

The STRIVE platform emphasizes conducting trials across the spectrum of disease severity for hospitalized patients. Two common scenarios will lend themselves to co-enrollment: (1) a participant is eligible for two trials at the same time (e.g., on admission) and the trials permit simultaneous enrollment (e.g., two comparative effectiveness trials in which the possibility of drug-drug interactions have been previously studied); and (2) a participant is enrolled in a STRIVE trial early in the hospital admission, completes the initial trial therapy, with subsequent eligibility for another trial if the patient does not recover or worsens. For example, patients could be randomized into a STRIVE trial early during their hospital admission for COVID-19 while on low-flow oxygen. Patients who then deteriorate and receive more intensive oxygen support (e.g., HFNC, NIV, IMV, ECMO) may be eligible for different STRIVE trials using agents in the same or different intervention classes.

Patients should be allowed to enroll in subsequent trials as long as they meet the eligibility criteria for that trial. Clinicians may hesitate to offer a trial targeting less-sick patients if they think the patient is likely to worsen and become eligible for a different STRIVE trial with a promising intervention. Conversely, a trial only enrolling participants who are more severely ill may only enroll those who are *admitted* in a more severe state (rather than deteriorating after admission) if there is another STRIVE trial for less acutely ill patients and co-enrollment is not permitted.

In general, there is strong scientific rationale for encouraging co-enrollment of Phase 3 trials of pre-licensure, investigational agents with trials evaluating interventions already administered within usual care. Co-enrollment leads to random assignment and systematic recording of these co-interventions rather than haphazard assignment based on clinical judgment. Co-enrollment in two trials of pre-licensure investigational agents may pose more challenges. In general, co-enrollment will be avoided when there is reason to believe that there is an important interaction between interventions or study procedures in the two trials that unacceptably increases the risk of one or both of the interventions or if there is mechanistic incompatibility, e.g., the two drugs are expected to antagonize each other in an important way.

Two main statistical considerations are relevant to co-enrollment: safety monitoring and efficacy analyses. These are discussed in the master protocol statistical analysis plan and trial-specific appendices.

6.2 Randomization and Stratification

We describe below how randomization will be conducted when there is a single trial open for enrollment (Section 6.2.1) and when multiple trials are open for enrollment (Sections 6.2.2 and 6.2.3).

When multiple trials are open, participants may become eligible for more than one trial at either the same time or at different times throughout their hospitalization. Whether and how randomization/co-enrollment may proceed in each of these settings will be discussed in each trial-specific appendix. Considerations will include whether agents are pre- or post-licensure, the safety profile of the agents, and potential drug-drug interactions, among other concerns.

6.2.1 Single Trial Open for Enrollment

When only a single trial is enrolling (or a participant could only be eligible for a single trial regardless of disease progression), patients will be equally allocated to each intervention + SOC in that trial unless specified differently in a trial-specific appendix. For example, for a study of a single investigational (pre-licensure) agent, participants will be randomized in a 1:1 ratio to the investigational agent + SOC or placebo + SOC. Trials of post-licensure agents could study two or more active agents (with or without placebo) + SOC (i.e., comparative effectiveness trials). The randomization allocation ratio may differ from 1:1 for some trials and the rationale for this will be given in the trial-specific appendix.

6.2.2 Multiple Trials Open for Enrollment and Participants Eligible for Multiple Trials Simultaneously

The master protocol outlines three potential approaches for participants who may be eligible for multiple trials at one time. Although each of the following could apply to each trial type outlined in Section 6.1, certain trial designs lend themselves more naturally to each approach to handle eligibility for multiple trials simultaneously which we note below.

(a) Factorial randomization (co-enrollment across trials)

If a participant is eligible for multiple trials simultaneously, the participant may be randomized to each trial separately (i.e., factorial randomization). For example, if there are two investigational agents (A and B - studied in two trials and both are placebo-controlled) for which the participant is eligible, the participant would be randomized 1:1 to investigational agent A or placebo and then randomized again to investigational agent B or placebo. In this randomization, one quarter of participants would each receive both active agents simultaneously, active agent A and placebo for B, active agent B and placebo for A, and both placebos.

This is equivalent to permitting simultaneous co-enrollment across the multiple trials for which the participant is eligible. As noted in Section 6.2, co-enrollment is conceptually most straightforward for comparative effectiveness trials or trials of re-purposed agents in which the possibility of drug-drug interactions have been previously studied. For example, participants in the TESICO trial are randomized using a factorial design to aviptadil or placebo and remdesivir or placebo.

Version 1.0, 11th November 2022 US IND# 162149

(b) Shared control/placebo

In some contexts, we would want to ensure that participants do not receive multiple active agents simultaneously. However, it might be possible for multiple trials to share a control group to improve efficiency. For example, if there are two investigational agents for which the participant is eligible, the randomization allocation could be 1:1:1 to investigational agent A + SOC, agent B + SOC, or placebo + SOC if the placebos for A and B were the same. If the two investigational agents (A and B) require different placebos (for example, when infusion volumes or drug delivery differ), equal allocation for treatment groups will be achieved through a two-step randomization procedure: in step 1, the participant is randomized 1:1 to trial A or trial B; in step 2, the participant is randomized 2:1 to the corresponding active agent or matching placebo (e.g., if the participant is randomized to trial A they would then be randomized 2:1 to investigational agent A + SOC or "agent-specific placebo for A" + SOC). With k trials, this can be viewed as an initial equal allocation to one of the k trials, followed by a second, k:1 allocation to the corresponding active agent or matching placebo.

Sites will be informed of the specific investigational agent/matching placebo (e.g., A or B) to which the participant was randomized (see Section 6.2).

Under this randomization framework, it is anticipated that the control groups will be pooled together for at least the efficacy analyses. A participant receiving the control condition would contribute to the analysis of both agents A and B only if the participant were eligible (and consented to) both agents A and B. Depending on the similarity of the matching placebo and approach to capture of safety data, the control groups may also be pooled together for safety analyses.

If investigational agents are added or dropped, the allocation ratio to active versus placebo will be appropriately modified, and overall sample size will be recalculated as appropriate.

This strategy is most appropriate for Phase 3 trials of pre-licensure, investigational agents and placebo-controlled trials of approved agents used off-label. For example, in the TICO platform, multiple monoclonal antibodies were studied simultaneously using a shared placebo group. Because sites will know which investigational agent/matching placebo the participant was allocated to, careful assessment of evolving possible differences in co-medication based on this knowledge, should also be evaluated when considering using a pooled control/placebo group. This allocation strategy only results in efficiency gains to the extent that there is overlap in the eligibility criterial among the trials. Thus, the eligibility criteria should be broadly similar among the trials for this allocation strategy. Finally, in order to pool data among the control conditions, the data collection schedule needs to be harmonized across the agents.

Comparative effectiveness trails of multiple evidence-based agents without a placebo-group would be more difficult to incorporate in this framework.

(c) Separate trials

Co-enrollment across the trials may not be permissible, and the mechanism of drug delivery and other considerations may preclude sharing a control group across multiple active agents. In this case, with k trials, participants will be initially equally allocated to one of the k trials,

US IND# 162149

followed by a second (equal) allocation to the corresponding agents/placebo being studied in that trial. Data will not be pooled between the different trials for any efficacy and safety analyses. For example, in the TICO platform, when the study agent required continuous infusion for 5 days, its placebo was sufficiently different from the placebo for the monoclonal antibodies (one or two infusions for an hour) that this was considered a separate trial.

6.2.3 Multiple Trials Open for Enrollment and Participants Eligible for Multiple Trials on Different Study Days

Participants may be eligible for multiple trials on different study days as their clinical condition changes. In this case, participants may co-enroll across multiple trials. For participants who co-enroll across multiple trials, the randomization will be independent in each trial as specified in the trials. Eligibility for certain agents may preclude co-enrollment into other trials due to safety or drug interactions. Unless specified in the trial-specific eligibility criteria, it is assumed that co-enrollment into multiple trials in the STRIVE platform is permitted.

6.2.4 SMART Design

This master protocol permits study of strategies of treatments given over time (i.e., dynamic treatment regimens or adaptive intervention strategies) through "strategy trials" or SMART. In these trials, at least some participants undergo a randomization across at least two different timepoints as their clinical condition changes. The multiple randomizations are explicitly specified in the trial-specific appendix (as opposed to two separate trials which allow for coenrollment). In general, participants should not be randomized to a single strategy upfront but should be randomized each time their condition changes.

A SMART design would be considered a single trial in the platform even though it may involve multiple randomizations. Therefore, participants will consent to the trial and not specific randomizations within the trial. Details on informed consent are given in Section 12.3.

6.2.5 Stratification

Randomization will usually be stratified by study site pharmacy, and severity of disease at entry unless stated otherwise in the trial-specific appendix. Severity of disease is determined by the respiratory infection or syndrome being studied. For example, strata that define disease severity for COVID-19 are based on supplemental oxygen use at randomization such as 1) invasive mechanical ventilation (IMV) or extra corporal membrane oxygenation (ECMO), 2) high-flow nasal cannula (HFNC) or non-invasive ventilation (NIV), 3) less than HFNC/NIV.

Within each stratum, mass-weighted urn randomization will be used to generate the active and placebo assignments. This will ensure the desired treatment allocation ratio is maintained throughout the trial.

6.3 Blinding

Investigational agents or placebo (as necessary) will be prepared by a pharmacist or equivalent, who is not blinded to the treatment assignment. All other study staff, including those at sites and those in roles spanning multiple sites or spanning the protocol as a whole, will be blinded unless otherwise specified (section 10.4).

Version 1.0, 11th November 2022

US IND# 162149

When more than one investigational agent is available for randomization, the clinical staff will be informed to which investigational agent/placebo the participant was randomly assigned for administration, but they will be blinded to whether the random assignment was to the active investigational agent or matching placebo.

If the blind is broken for safety reasons, this will be documented. In that situation, every attempt will be made to minimize the number of people unblinded. See also section 10.4; specific unblinding procedures and instructions are found in the PIM.

6.4 Sample size and Statistical Considerations

For the endpoints considered, for any single trial, sample size will have to consider the target population (this may include the variant) and the treatment being studied (e.g., adherence).

This section provides illustrative sample size estimate examples for each of the three primary outcomes defined in section 4.1, under a range of assumptions. All sample size estimates below are for superiority trials, comparing a given investigational agent versus its control arm. For each trial, the specific sample size estimate and the assumptions used will be described in detail in the trial-specific appendix.

The following assumptions are used for each of the three outcomes:

- a. Treatment and control groups are of equal size (1:1 randomization).
- b. The primary analysis will by intention to treat.
- c. The type 1 error is set at 0.025 (one-sided). If several agents are investigated in parallel, each pairwise comparison of investigational agent versus placebo is considered a separate trial, and the type 1 error will not be adjusted for the number of comparisons. In specific cases, such as a trial with two or more co-primary comparisons, a type 1 error adjustment may be considered and would be described in the trial-specific appendix. Lower Type 1 error limits require higher sample sizes.

6.4.1 Primary Outcome: Mortality

The primary outcome of all-cause mortality, typically through Day 60; in this section, we provide sample size estimates for assumed cumulative mortality rates of 20%, 30%, and 40% by Day 60, and a range of hypothesized treatment effects corresponding to hazard ratios between 0.65 and 0.80.

The following assumptions were used, in addition to assumptions a-c above:

- d. Treatment groups will be compared for time to death using a log-rank test. Comment: Estimated sample sizes change only minimally if replacing the log-rank time-to-event analysis by a comparison between treatment groups of the cumulative proportions of participants who died by Day 60 using logistic regression; cumulative proportions in the two treatment groups corresponding to given hazard ratios are summarized in Table 6.1 below.
- e. Power is set at 80% or 90% to detect a hazard ratio of 0.80, 0.75, 0.70, or 0.65 for time to death comparing the investigational treatment versus control. This corresponds to decreases in the relative hazard of mortality of 20%, 25%, 30% and 35%, respectively.

US IND# 162149

We chose these hypothesized treatment effects to cover a range of plausible values: decreases of less than 20% in relative hazard require prohibitively large sample sizes and may be less clinically relevant (e.g., hazard ratio of 0.80 corresponds to a decrease from 30% mortality in the control group to 24.8% in the treatment group, an absolute difference of 5.2%); conversely, it would be difficult to achieve more than 35% reduction in mortality with any single treatment.

- f. With these assumptions for type 1 and type 2 error, and treatment effects corresponding to hazard ratios between 0.65 and 0.80, the needed total number of events is shown in the first row of Table 6.1 below. For example, 252 primary events are sufficient to detect an HR of 0.70 with 80% power.
- g. The total sample size needed to accrue the required number of events depends on the underlying rate of mortality in the control group. Table 6.1 summarizes the total sample size needed for cumulative mortality rates of 20%, 30% and 40%, respectively, inflated by 5% to account for withdrawal of consent or loss to follow-up. For example, given a mortality rate of 30% in the control arm, a total sample size of 1016 participants is sufficient to detect an HR of 0.70 with 80% power.

Table 6. 1. Estimated Total number of Events Needed to Detect Differences in Mortality Between the Treatment and Control Groups. For hazard ratios (HR) of 0.65, 0.70, 0.75, and 0.80 with 90% power, and total sample size needed assuming cumulative mortality rates of 20%, 30% and 40%, respectively.

respectively.	Hazard Ratio (Agent versus Control)				
	HR=0.65	HR=0.70	HR=0.75	HR=0.80	
Total number of events, 80% power	175	252	385	636	
90% power	234	338	515	851	
Event rate control (%)	20.0	20.0	20.0	20.0	
Event rate agent (%)	13.5	14.5	15.4	16.3	
Total sample size, 80% power	1094	1537	2283	3675	
Total sample size, 90% power	1466	2058	3053	4918	
Event rate control (%)	30.0	30.0	30.0	30.0	
Event rate agent (%)	20.7	22.1	23.5	24.8	
Total sample size, 80% power	690	1016	1512	2436	
Total sample size, 90% power	968	1361	2022	3261	
Event rate control (%)	40.0	40.0	40.0	40.0	
Event rate agent (%)	28.3	30.1	31.8	33.5	
Total sample size, 80% power	512	756	1126	1816	
Total sample size, 90% power	720	1012	1506	2432	

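### In Table 6.1 the sample sizes 690 and 512 (HR 0.65, 80% power, 30% and 40% control mortality) leave out the 5% inflation that assumption g says was applied

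*Protocol*

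**What the plan says.** Section 6.4 of the protocol sets a one-sided type 1 error of 0.025 and 1:1 allocation for all the sample size examples. Section 6.4.1 adds for mortality: "Treatment groups will be compared for time to death using a log-rank test", with 80% or 90% power and hazard ratios from 0.65 to 0.80. Table 6.1 gives the events needed, "Total number of events, 80% power 175 252 385 636" for HR 0.65, 0.70, 0.75 and 0.80 in that order, and then total sample sizes for control mortality of 20%, 30% and 40%.

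Assumption g states that these totals are "inflated by 5% to account for withdrawal of consent or loss to follow-up" and exempts no cell. Its worked example is 1016 participants for HR 0.70, 30% mortality and 80% power.

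The two rows at issue read "Total sample size, 80% power 690 1016 1512 2436" for 30% control mortality and "Total sample size, 80% power 512 756 1126 1816" for 40%. The first entry in each row is the HR 0.65 figure. No footnote marks it as calculated differently.

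**The concern.** The printed totals can be checked against one another without any sample size formula. For a fixed hazard ratio and control mortality, the ratio of the 90% power total to the 80% power total should not change across the table. In ten of the twelve pairs it is 1.337 to 1.340 (for example 1361/1016 = 1.340 and 1466/1094 = 1.340). In the other two it is 968/690 = 1.403 and 720/512 = 1.406. Either the 80% figures are too low or the 90% figures are too high.

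If the 80% figures are the ones that lack the allowance for losses, someone designing a trial would take them as already covering 5% loss and would not add it again. Section 4.1.1 directs trials with expected mortality above 20% to Section 6.4.1, and both cells lie in that range.

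**Working it through.** **Inputs.** From Section 6.4: one-sided 0.025, 1:1 allocation. From Section 6.4.1 and Table 6.1: log-rank test, power 80% or 90%, the hazard ratios, control mortality of 20%, 30% and 40%, the printed event counts, and the 5% inflation.

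**Step 1: reproduce the event counts.** Freedman's formula is events = (z_0.975 + z_power)² × ((1 + HR)/(1 − HR))². At 80% power the first factor is 7.849.

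- HR 0.65: 7.849 × (1.65/0.35)² = 174.4 (printed 175).
- HR 0.70: 7.849 × (1.70/0.30)² = 252.0 (printed 252).

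All eight printed counts agree to within one event. Schoenfeld's formula gives 169.2 for HR 0.65 at 80% power, so it is not the one used.

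**Step 2: reproduce the worked example.** Agent rate = 1 − (1 − control rate)^HR = 1 − 0.7^0.70 = 0.2209. The mean of this and 0.30 is 0.2605. Then 252/0.2605 = 967.5 (unrounded rates), and × 1.05 = 1015.8, printed as 1016. Dividing by 0.95 instead gives 1018.4, so the table multiplies by 1.05.

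**Step 3: apply the same rule to the HR 0.65 column.** Agent rates are 0.1350, 0.2069 and 0.2825.

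| Control mortality | Power | Events | Events / mean rate | × 1.05 | Printed | Printed / uninflated |
|---|---|---|---|---|---|---|
| 20% | 80% | 175 | 1044.7 | 1097.0 | 1094 | 1.047 |
| 20% | 90% | 234 | 1397.0 | 1466.8 | 1466 | 1.049 |
| **30%** | **80%** | **175** | **690.4** | **725.0** | **690** | **0.999** |
| 30% | 90% | 234 | 923.2 | 969.4 | 968 | 1.049 |
| **40%** | **80%** | **175** | **512.8** | **538.4** | **512** | **0.998** |
| 40% | 90% | 234 | 685.7 | 720.0 | 720 | 1.050 |

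Over all 24 cells, 22 have a ratio between 1.047 and 1.051. The 1.047 arises only because 174.4 events were rounded up to 175. With unrounded events the 22 cells lie between 1.050 and 1.052, and the two exceptions are 690/688.2 = 1.003 and 512/511.1 = 1.002.

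**Step 4: consequence if 5% are lost and contribute no deaths.**

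- 30% mortality: 690 × 0.95 × 0.2535 = 166.1 deaths.
- 40% mortality: 512 × 0.95 × 0.3413 = 166.0 deaths.

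Power = Φ(√deaths × 0.35/1.65 − 1.96), which gives 78.1% and 78.0%. If half of the loss takes effect, power is about 79.1%. With no loss the deaths are 174.9 and 174.7, and both cells give 80.1%.

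**Step 5: check the corrected values.** With 725 and 538 and a 5% loss, expected deaths are 174.6 and 174.4, and power is 80.0% in both.

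**The case against.** The strongest objection concerns weight, not arithmetic. Section 6.4 presents these figures as illustrations and leaves each trial's sample size and assumptions to its trial-specific appendix. The Protocol Summary says the same, and the appendix template has its own sample size section. No trial in this document is sized at 690 or 512. HR 0.65 is also the optimistic edge of the grid: assumption e doubts that a single treatment could do better. Section 6.4.4 requires blinded re-estimation before enrollment ends, using pooled outcomes, withdrawals and missing data, and the event target of 175 is itself printed correctly. All of this stands, and it makes the point minor.

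A reader might infer that a trial starting from these cells will end short of 175 deaths, or that its power simply is 78%. The documents do not support either. Re-estimation is aimed at exactly such a shortfall. The 78% needs the full 5% to be lost without contributing any deaths, whereas a log-rank analysis uses follow-up up to censoring and Section 4.1.2 commits to finding vital status through the end of follow-up.

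A different formula does not rescue the two cells. Schoenfeld's events with 5% inflation would give about 701 and 521, and a two-proportion calculation about 718 and 536, so neither yields 690 and 512. The 90% power cells for the same hazard ratio and mortality (968 and 720) are inflated. A misread digit is also unlikely, since both printed values lie within one participant of the uninflated result.

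**Conclusion.** Two of the 24 totals in Table 6.1 contradict assumption g: 690 and 512 are uninflated figures in a table described as inflated. They are low by 35 and 26 participants (725 − 690 and 538 − 512), about 5% each. The cost is at most about 2 percentage points of power, on the assumptions of Step 4, and less with partial follow-up. The result rests on Freedman events and a × 1.05 factor, both of which the table's other entries confirm.

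This is a minor correction. It touches no event target, test, monitoring boundary or trial defined in the document, and it gives no reason to doubt the other 22 totals.

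**What to change.** In Table 6.1, HR 0.65 column, 80% power, replace 690 by about 725 (30% control mortality) and 512 by about 538 (40% control mortality). Both are the printed 175 events divided by the mean event rate, times 1.05. Working from unrounded events would lower each by one or two participants. Assumption g and all other entries can stay as they are.

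The cost is two numbers at the next protocol version, with no change to design or analysis. Any trial-specific appendix that has taken either figure over should be checked at the same time.
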